10.2.4 Brain structural Imaging with Voxel Based Morphometry (VBM)

We have published extensively using VBM methods in various chronic pain states.¹⁷⁸⁻¹⁸¹ In brief, our protocol includes T1-weighted structural images (TR 2400/TE 2.14ms; Flip angle 8 deg; FOV 224X224; Voxel size 0.8mm isotropic) segmented into white matter (WM), gray matter (GM), and cerebral spinal fluid using the

segment function in SPM12, running under MATLAB 2017a. The resulting GM segments are then processed using the diffeomorphic anatomical registration through exponentiated lie algebra (DARTEL) toolbox.¹⁸² We will normalize VBM data to standard space. We will smooth normalized, modulated images with a Gaussian kernel, and pass individual participant maps up to group level analysis.

Group Level Analyses: We will enter smoothed GM images into a multiple regression model in SPM12 with change in pain interference (post minus pre-treatment) as the covariate of interest. Age and total brain volume will be entered as nuisance regressors. We will exclude voxels with GM values < .1 from analysis.

Feasibility: We anticipate few problems in data analysis based on our past studies.^{154,178-181}

Feasibility and Anticipated Neuroimaging Results. We have published extensively in the field of fcMRI, evoked pain fMRI, and ¹H-MRS, and expect no issues with data acquisition or analyses.^{102-104,115,129,136,142-144,146,155,156,168,183-186}

10.3 Biospecimen Collection for Inflammation Methods

No more than 10mL of blood will be collected at each deep phenotyping visit. All samples will be stored initially at the University of Michigan but may be sent to other MRCs or central biorepositories for future storage or additional analyses.

Stimulated Assays. The TruCulture system (Myriad RBM) consists of small vacutainers preloaded with immune stimulants (e.g., LPS) or control media into which whole blood is drawn. Following incubation in a small table-top unit, the supernatant is isolated without the need for centrifugation using a small plunger included in the kit. Whole blood is drawn via venipuncture into two different 1 mL tubes containing lipopolysaccharide (LPS; 100 ng/mL), or media (NULL). LPS is potent agonist of TLR4.¹⁸⁷ Samples are immediately incubated at 37° C for 24 hours, after which the supernatant is isolated with a valve separator included in the kit. The supernatant is frozen at -80° C prior to shipment to a biorepository where it is thawed, aliquoted into 0.25 mL containers, and stored at -80° C for batch analysis. All batches include control standards (i.e., samples provided by lab personnel) to allow for estimation of batch effects.

Cytokine/Chemokines are analyzed from supernatant using multiplex Luminex xMap technology or equivalent. We have completed a series of dilution protocols to determine optimal concentrations to keep each analyte in the dynamic range of the assays. A minimum of seven cytokines/chemokines will be analyzed from each sample including those in the pro-inflammatory NF-κB- mediated suite (IL-1β, IL-6, TNF-α), chemotactic cytokines (IL-8, MCP-1, MIP1α), and regulatory cytokine IL-10.

Analyses: Cytokine/chemokine data often does not follow a normal distribution, which can create issues when using parametric statistical approaches. Therefore, we will evaluate normality with the Shapiro-Wilk test statistic and apply Box-Cox transformations where required. Any values below the lower limit of detection will be set to half that value. Multi-level models will be employed that can accommodate random effects for each batch analysis (in case significant variation is observed between-batches), and for site of collection.

Feasibility and Anticipated Results. The protocol developed for MAPP serves as a template for this proposal because we have demonstrated that the procedures can be implemented with minimal training and without the need for dedicated wet lab space at the site of collection. In the second phase of MAPP, more than 95% of participant visits have resulted in analyzable samples across all three conditions. The stimulated assays are also clearly effective: in 198 samples from a preliminary MAPP II analysis, LPS-stimulated IL-6 showed a median increase of 21,000 pg/mL compared to media (unstimulated condition) while LPS-stimulated MIP1a showed a median increase of 48,000 pg/mL over media. We have also conducted a small analysis of freeze/thaw cycles as two such cycles are currently required for this protocol. After eight cycles, there was no evidence of change in analyte (e.g., IL-6, IL-1) levels.

Gene expression. Approximately 2.5mL of whole blood is drawn into the PaxGene® blood RNA collection tubes containing approximately 6.9mL of proprietary stabilizing reagent. The tube is gently inverted 8-10 times and allowed to stand at room temperature for 2 hours at which point the same tube is frozen at -30-80° C for batch analysis.

Analyses. Differential gene expression will be assessed using standard linear statistical models including effects of any covariates such as age and gender. We will identify all gene transcripts based on thresholding of >1.15-fold differential expression between treatment responders and non-responders.

Sex hormones. We may also collect 5 mL or less of blood into “red top” containers and allowed to clot for 15-30 minutes. Samples are then centrifuged for 10-20 minutes at 1000-2000 rcf for isolate of serum. These are subsequently aliquoted into .5-2 mL cryovials and stored at -80° C for batch analysis of hormones (e.g., testosterone, GnRH, LH and FSH).

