Group Level Analysis. Seed and network-to-whole-brain connectivity maps will be entered into a multiple regression model in SPM with change in pain interference (post minus pre-treatment) as a covariate of interest. Age and sex will be entered as covariates of no interest. Although not the primary objective of Aim 3, we will also conduct exploratory analyses to examine the mechanism of action of specific treatments. Changes in connectivity patterns following each of the phase 1 treatments will be performed using paired sample t-tests in SPM12. Resulting maps are thresholded at $p < .001$ uncorrected voxel threshold with $p \leq .05$ FDR significance corrected for multiple comparisons.

Graph Theory Analyses. Using Graph Theory Analyses the brain is defined as a network of 264 non-overlapping nodes (10 mm spheres) connected by edges or links.^{161,162} These nodes and the preprocessed fMRI data are entered into the Conn functional connectivity toolbox to create Fisher z-transformed bivariate correlation (Pearson's r) matrices (264 x 264) for each participant. To exclude weak or spurious connections, matrices are thresholded beginning with the strongest 5% connections and proceeding in steps of 5% up to 40% density, resulting in binary undirected graphs containing the most significant edges. Using the Brain Connectivity Toolbox,¹⁶³ we will calculate the following graph theoretical measures to assess global (efficiency, modularity, rich-club) and nodal (hub status) network properties, as previously published.¹⁶⁴ To assess hub status, we will calculate eigenvector centrality which takes into account the connectedness of a node, in addition to the connectedness of that node's neighbors. Hub status will be assigned to a node if the eigenvector centrality is greater than one standard deviation above the group mean.^{165,166}

Group Level Analysis. We will determine if hub status and rich club organization predicts treatment response. Individual hub measures will be entered into regression analyses to predict ($p < .05$) association with change in pain interference pre- versus post-treatment.

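### Gene transcripts are identified on a 1.15-fold difference alone, so their false-positive rate is uncontrolled; the hub regressions also use an uncorrected p < .05

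*Protocol*

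**What the plan says.** **Transcripts.** The gene expression paragraph of Protocol 10.3 first gives a model: "Differential gene expression will be assessed using standard linear statistical models including effects of any covariates such as age and gender". It then gives the rule for naming a transcript: "We will identify all gene transcripts based on thresholding of >1.15-fold differential expression between treatment responders and non-responders". No p-value, q-value or confidence interval is attached to that rule. The paragraph does not define a responder and does not say whether the comparison is made within each arm or over all deep-phenotyped patients.

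**Hubs.** In the graph theory analyses of Protocol 10.2.1, "the brain is defined as a network of 264 non-overlapping nodes", and "matrices are thresholded beginning with the strongest 5% connections and proceeding in steps of 5% up to 40% density". A hub is a subset of nodes: "Hub status will be assigned to a node if the eigenvector centrality is greater than one standard deviation above the group mean". The group-level step is "Individual hub measures will be entered into regression analyses to predict ($p < .05$) association" with change in pain interference. No correction is stated, nor the number of tests, nor how the densities are combined.

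**Comparators.** The seed and network connectivity maps in 10.2.1 carry "FDR significance corrected for multiple comparisons", and the evoked-pain maps in 10.2.3 have the same rule. The voxel-based morphometry analysis in 10.2.4 states no threshold.

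**General policy.** SAP 7.5 declines formal multiplicity control because the trial looks for phenotype and treatment combinations to study later. It prefers intervals and effect sizes to p-values, with cross-validation where appropriate.

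**The concern.** A fixed fold change is an effect-size filter, not an error-rate rule. The same observed 1.15-fold difference can be strong evidence when a transcript varies little and the groups are large, and almost none when it varies a lot and the groups are small. The fitted models would supply the standard error that separates these cases, but the rule does not use it. The length of the list is then partly a function of assay noise, and a reader cannot tell what share of it to expect from chance.

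At stake is the credibility of an exploratory list of transcripts associated with response. The hub regressions raise a milder form of the same problem: each test has a nominal 5% level, but the number of tests is not given.

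**Working it through.** **A stated figure first.** The documents give no expected number of false findings. The nearest figure is the power for the deep subset in Protocol 18.1.5: 81% at r = 0.43, n = 40, two-sided 5%. By Fisher z, Φ(atanh(0.43) × √37 − 1.96) gives 79.9%, and a bias-corrected version gives 80.7%. It reproduces, and n = 40 per arm is used below.

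**Transcripts: inputs**
- Threshold: log2(1.15) = 0.2016. The rule is read as a difference in either direction; upward only would halve the percentages.
- Group sizes: 40 per treatment and 160 in all (Protocol 18.1.5).
- Responder share: 30%, from the expectation in 18.1.5 that at least that share shows a 50% improvement, or a median split, one of the two options in the machine-learning paragraph of 10.2.1. Neither is stated for gene expression.
- SD of log2 expression: 0.3 to 0.7. **Assumption**; the documents give none.

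**Formula.** With no true difference, SE = SD × √(1/n1 + 1/n2), and the chance of passing is 2 × [1 − Φ(0.2016/SE)]. This is a normal approximation that ignores covariates.

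Example, 12 versus 28 at SD 0.3: √(1/12 + 1/28) = 0.345; SE = 0.1035; 0.2016/0.1035 = 1.95; two-sided tail 5.1%.

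| Responders / non-responders | SD 0.3 | SD 0.5 | SD 0.7 |
|---|---|---|---|
| 12 / 28 (one arm, 30%) | 5.1% | 24.2% | 40.4% |
| 20 / 20 (one arm, median split) | 3.4% | 20.2% | 36.2% |
| 48 / 112 (pooled, 30%) | 0.01% | 1.9% | 9.5% |
| 80 / 80 (pooled, median split) | 0.002% | 1.1% | 6.8% |

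At SD 0.5, a transcript lying exactly on the threshold has p of about 0.25 in the 12/28 split and about 0.02 in the 48/112 split.

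**Effect of adding FDR.** In 20 simulated runs with 10,000 independent null transcripts (an assumed count), the fold rule alone passed on average about 510, 2,420 and 4,040 transcripts at SD 0.3, 0.5 and 0.7 (12/28), and about 1, 190 and 950 (48/112). Fold change plus Benjamini-Hochberg at 5% passed 0 to 0.15 on average.

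**Hubs**
- All nodes tested: 264 × 0.05 = 13.2 expected false hits.
- Only hub nodes tested: if centrality is roughly normal, about 16% of nodes lie more than 1 SD above the mean. That is about 42 nodes, and 42 × 0.05 = 2.1.
- Densities from 5% to 40% in steps of 5% make eight graphs. If each is tested separately, the totals are 8 × 13.2 = 105.6 or 8 × 2.1 = 16.8.

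These expected counts assume that no node has a true association. Correlation between nodes changes their spread, not their mean.

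**Power cost for hubs, upper bound.** With Bonferroni, power at r = 0.43 and n = 40 falls from 80% to 17% (264 tests, level 0.05/264 = 0.00019) or 33% (42 tests, level 0.05/42 = 0.0012). With all 160 patients it is 98% or 99%. FDR costs less than Bonferroni.

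**The case against.** The strongest reply is SAP 7.5. Multiplicity control is waived openly, for a stated reason, and with low power acknowledged. Protocol 18.1 also labels its mechanistic analyses exploratory.

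For the hub regressions much of this stands. The power figures above show a real trade-off, so the request there is for disclosure rather than a stricter decision rule. For transcripts it carries less weight. The SAP's reasoning concerns phenotype-by-treatment interactions, and transcripts are not among the deep modifiers in SAP Tables 3 and 5. The SAP also promises measures of uncertainty, which the fold rule lacks.

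Four stronger readings might be inferred, and the documents do not support them:
- **That 264 hubs are tested.** 264 is the number of nodes, hubs are a subset, and the number of tests is not stated.
- **That the lists would be mostly noise.** This depends on the SD, the transcript count, the pooling and the number of true effects, none of which is given. Pooled at SD 0.3, about 1 null transcript in 10,000 passes.
- **That the lists feed the predictive panels.** Protocol 18.2.2 has priority variables flagged for model building but names neither transcripts nor hubs, and one of its examples requires family-wise correction. The variable selection in SAP 9.2 uses light-phenotype data only. Protocol 18.1.5 adds penalised regression and cross-validation.
- **That every voxel map uses FDR.** The morphometry analysis states no threshold, and gene expression sits in a different section from the maps that do.

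**Conclusion.** The point holds for transcripts. The rule as written does not control the false-positive rate, although the models needed to control it are already planned. Under the assumed SDs the share of null transcripts passing is about 3% to 40% per arm and about 0% to 10% pooled. The supportable statement is that the rate is uncontrolled, not that it is always high.

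For hubs the point is secondary. Between about 2 and 13 false hits are expected per analysis, and per density if densities are tested separately. The range reflects an unstated number of tests and, at its lower end, a normal assumption for centrality. The missing correction is inconsistent with the FDR rule for the connectivity and evoked-pain maps, but it falls within a disclosed exploratory policy.

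Neither part touches the primary endpoint or its analysis.

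**What to change.** **Transcripts (Protocol 10.3).** Identify transcripts by an FDR of at most 5% from the planned linear models, and keep the 1.15-fold difference as an additional filter. State how a responder is defined and whether the comparison is per arm or pooled. Label the list exploratory, and report the full ranked list with estimates and q-values so that nothing is lost for later work.

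**Hubs (Protocol 10.2.1).** State which nodes are tested and whether densities are tested separately. Report FDR q-values across the nodes tested, and across densities if separate, beside the nominal p-values. Add that SAP 7.5 waives formal control for exploratory aims.

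**Cost.** A few sentences of text, with no new data and no new models. The transcript list becomes shorter and some power is lost. That loss cannot be quantified without an SD and a transcript count. For hubs, showing q-values beside p-values leaves the nominal results available.

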10.4 Unscheduled Non-Study Interventions Triggering Deep Assessments

It is anticipated that 10-20% of enrolled participants will get a non-study related invasive or minimally-invasive pain intervention including back surgery, epidural steroid injections or facet joint injections while enrolled in the study. To assess these common pain medicine interventions that take place outside of the study, monthly assessments will ask about plans for new treatments and also request that participants contact study staff if one of these treatments is scheduled. Participants who meet the deep phenotyping inclusion criteria will be offered an additional deep assessment visit **prior to** the medically scheduled pain intervention. Should the participant agree, then a deep phenotyping visit will be scheduled at the CPFRC to take place in advance of the intervention. Data will also be collected exploring why the patient chose to undergo this non-study intervention (e.g., not satisfied with current treatments, physician prescribed new treatment). Then, at 4 and 8 weeks after the non-study intervention participants will undergo a separate follow-up assessment (same as that used for the BACPAC consortium non-study intervention surveillance, see Section 11 below).

11 Other Unscheduled, Non-Study Interventions (NSI) Follow-Up Assessments

Other non-study interventions (NSI) are expected to occur during the course of a patient’s enrollment and will be assessed once per month for the first 6 months of study enrollment during T1-T4 and during mini-assessments as appropriate. An affirmative response regarding starting one of these NSI will trigger a short follow-up questionnaire assessment consisting of a Patient Global Assessment of Change (PGIC), pain intensity as measured by PROMIS Pain Intensity and the Low-Back Pain Specific Pain Intensity, and the PROMIS Pain Interference (4a) delivered via Qualtrics at 4 weeks and 8 weeks after the treatment. We will also assess the reasons for starting the new treatment. These follow-up assessments will only be triggered for the first NSI scheduled for a participant. Later NSIs will only be logged and inform data analysis. Treatments that will trigger these follow-up assessments are listed below:

1. Spinal fusion
2. Injections for low back pain
3. Changes to medication for low back pain
4. Spinal adjustment/manipulation, physical therapy or occupational therapy supervised by a chiropractor, physical therapist or occupational therapist, or direct non-medication treatment such as ultrasound or diathermy for low-back pain
5. New exercise routine to manage back pain
6. Acupuncture
7. Mental health therapy or counseling
8. Mindfulness, meditation or relaxation
9. New diet or weight loss program
10. Any other new non-study treatment for low back pain

12 Study Measures and Questionnaires

Validated questionnaires will be used to assess many of the variables of interest. The measures and their assessment time points are depicted in Section 1.3. Questionnaires will be completed by participants at all visits T1-T5 and there will be additional mini-assessments described below. Additionally, study surveys will be completed by participants in the MBSR and physical therapy interventions (see sections 9.1 and 9.2).

12.1 Mini-Assessments

Participants will also be asked to complete electronic questionnaires every 2 weeks throughout the study. There are a total of 17 mini-assessments and those in weeks 1, 6, 15, 24 and 36 will be completed as part of the study visit survey (T1-T5). There will be 12 additional mini-assessments will take place at weeks 3, 8, 10, 12, 17, 19, 21, 26, 28, 30, 32 and 34. There are three types of mini-assessments- standard, expanded and mediation and these are described below.

12.1.1 Standard Mini-Assessments

There are 10 standard mini-assessments and they are done at assessments done at weeks 3, 8, 10, 17, 21, 26, 28, 30, 32, and 34. These will be sent electronically to participants through Qualtrics.

12.1.2 Expanded Mini-Assessment

There will be an expanded version of the mini-assessment that takes place close to 3 months (week 12 after baseline). The expanded version at week 12 will include added measures to comply with BACPAC minimum dataset requirements.

12.1.3 Mediation Mini-Assessment

There will be a mediation mini-assessment at week 19. This will have the same surveys as the standard and expanded mini-assessments. Additionally, there will be 3 surveys not in the other assessments. These are described in Section 1.3.

13 Subject Incentives

Table 4 Breakdown of Participant Incentives for Study Activities

Subjects will receive incentive payments upon completion of each study visit and will be eligible for a total payment of up to \$1370. Participants can receive up to \$600 for the light phenotyping, up to \$500 for the deep phenotyping, up to \$260 for an unscheduled deep phenotyping visit and \$10 for an unscheduled non-study intervention follow-up assessment (see Table 4 Breakdown of Participant Incentives for Study Activities).

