# Statistical Analysis Plan

Table 1 Schedule of Assessments

	Scheduled												Unscheduled Visits					
	Pre-screening (-30days)	Study Visit T1 (Week 1)	Ecological Momentary Activity (EMA)-1 (Week 1)	Study Visit T2 (Week 6)	Deep Visit 1 * (Week 6)	Ecological Momentary Activity (EMA)-2 (Week 6)	Intervention 1 (Weeks 7-14)	Study Visit T3 (Week 15)	Deep Visit 2 * (Week 15)	Ecological Momentary Activity (EMA)-3 (Week 15)	Intervention 2 (Weeks 116-23)	Study Visit T4 (Week 224)	Ecological Momentary Activity (EMA)-4 (Week 24)	Ecological Momentary Activity (EMA)-5 (Week 36)	Study Visit T5 (Week 36)	10 Mini-assessments (Weeks 3, 8, 10, 17, 21, 26, 28, 30, 32, 34)	1 Expanded Mini-assessment (Week 12)	1 Mediation Mini-assessment (Week 19)
EMR Eligibility Review	x																	
Screening Eligibility Review	x	x																
Informed Consent		x																
Charlson Comorbidity Index (CCI)		x																
Demographics	x																	
Medical History and Medications	x		x				x				x			x				
Vitals, Height & Weight	x		x				x			x			x					
Biomechanical, Physical Exam & Physical Function Measures																		
2-Minute Walk Test (2MWT)		x		x			x			x		x		x				
4-Meter Walk Gait Speed Test (from SPPB)																		
Timed Sit-to-Stand (STS)																		

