### 9.3 Objective 3 Analysis Plan

**Objective 3:** Identify the mechanisms that explain the causal treatment effects.

The primary analysis for the exploratory objective 3 (specific aim 2) will involve a series of mediation analyses in order to identify the mechanisms that underlie the differential treatment responses. This analysis will use light phenotyping data from T2 and the interim assessment conducted at the midpoint of the first-stage treatment period. Second-treatment stage data will not be used for this analysis. Investigators did not propose a light phenotyping-based mediator for the Duloxetine treatment. Thus, a mediation analysis based on light-phenotyping data will not be carried out for this study arm.

The study does not include a control group since each of the four therapies have been previously shown to be effective for treating cLBP. As a result, the mediation analyses will be conducted by treatment group. Within each treatment group, the proposed treatment modifier will play the role of the exposure in the mediation analysis. Hypothesized mediators were determined by the study investigators and are listed in Table 6 by treatment arm.

For example, consider the PT/Exercise treatment group. Investigators expect that individuals who both receive the PT/Exercise treatment and have lower self-perception of their own efficacy will respond better to the PT/Exercise intervention and have lower PROMIS Pain Interference scores at follow up. They believe that this effect is attributable in part to changes in the patients fear avoidance beliefs and avoidance behaviors. The mediation analysis will assess whether greater pain catastrophizing is associated with a greater reduction in fear avoidance beliefs, which leads to greater improvement in pain interference scores.

The outcome measure for each mediation analysis will be the PROMIS Pain Interference score measured at T3. The exposures and mediators will be measured at T2 and the first treatment-stage midpoint, respectively.

*Table 6 Hypothesized Mediation Analyses by Treatment.*

Treatment	Mediation Analysis Exposure (X)	Expected treatment mediator (M)
MBSR	PROMIS Pain Catastrophizing	Experiences Questionnaire Score
PT/Exercise	Pain Self-Efficacy Score	Fear Avoidance Beliefs Questionnaire
Acupressure	Fibromyalgia Screening Score	GSS-8

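### The only mediation mini-assessment falls at week 19, in the second treatment period and after T3, so it cannot supply the first-stage mediators that SAP 9.3 requires

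*Protocol*

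**What the plan says.** Protocol 12.1 lists twelve mini-assessments, at "weeks 3, 8, 10, 12, 17, 19, 21, 26, 28, 30, 32 and 34". Section 12.1.1 makes ten of them standard ("weeks 3, 8, 10, 17, 21, 26, 28, 30, 32, and 34"), and 12.1.2 makes week 12 the expanded version, with additions for the consortium's minimum dataset. Section 12.1.3 then says: "There will be a mediation mini-assessment at week 19". On its content it adds: "Additionally, there will be 3 surveys not in the other assessments". It does not name those surveys and refers to the schedule in Section 1.3. SAP Table 1 also heads its mediation column with week 19.

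SAP 9.3 plans one mediation analysis in each of three arms. Table 6 gives the mediators: the Experiences Questionnaire (EQ) for MBSR, the Fear Avoidance Beliefs Questionnaire (FABQ) for PT/exercise and the GSS-8 for acupressure. On data sources it says: "This analysis will use light phenotyping data from T2 and the interim assessment conducted at the midpoint of the first-stage treatment period". It continues: "Second-treatment stage data will not be used for this analysis". The outcome is PROMIS Pain Interference at T3.

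**The concern.** A mediator has to be measured after the exposure and before the outcome. SAP 9.3 respects that order: exposure at T2, mediator partway through the first treatment, outcome at T3. The one assessment labelled for mediation does not. By week 19 the T3 outcome has been recorded, and patients with PGIC of 2 or more at T3 have been re-randomized to a different treatment.

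SAP 9.3 names no week and no mini-assessment as its mediator source. If staff follow 12.1.3 literally, the mediator surveys may not be given at the time the analysis needs them, and a first-stage measurement that was missed cannot be recovered later.

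**Working it through.** **Inputs.** From SAP Table 1: Intervention 1 in weeks 7-14, T3 at week 15, Intervention 2 in weeks 16-23. (The printed Intervention 2 header has a stray leading digit; 16-23 is the reading that gives eight weeks after T3.) From SAP 5.6: visits T2-T5 may fall within 2 weeks either side of nominal. From Protocol 12.1 to 12.1.3: the mini-assessment weeks.

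**Is week 19 a misprint?** 10 standard + 1 expanded (week 12) + 1 mediation (week 19) = 12, and 12 + 5 visit surveys = 17, the total in Protocol 12.1. Removing the ten standard weeks and week 12 from the full list leaves only week 19. Protocol 12.1, Protocol 12.1.3 and SAP Table 1 agree on it.

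**Where week 19 falls.** Period midpoint = (first week + last week) / 2.

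- First period: (7 + 14) / 2 = 10.5
- Second period: (16 + 23) / 2 = 19.5
- Week 19 minus the first midpoint: 19 - 10.5 = 8.5 weeks
- Week 19 minus nominal T3: 19 - 15 = 4 weeks
- With T3 anywhere in weeks 13-17: 19 - 17 = 2 to 19 - 13 = 6 weeks

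Week 19 follows T3 even at the latest permitted T3.

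**What is available in weeks 7-14.** Weeks 8 and 10 (standard) and week 12 (expanded). Week 10 is treatment week 10 - 7 + 1 = 4 of 8, half a week from the midpoint. Week 12 is treatment week 6 of 8, 1.5 weeks from it. Neither is the mediation version.

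**Are the mediators collected there anyway?** The schedule columns are damaged, so I count marks per row rather than trust their positions.

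| Row | Marks, SAP Table 1 | Marks, Protocol 1.3 | Expected at visits | Left over (SAP / Protocol) |
|---|---|---|---|---|
| EQ-11 | 7 | 6 | 5 (T1-T5) | 2 / 1 |
| FABQ | 7 | 6 | 5 (T1-T5) | 2 / 1 |
| GSS-8 | 10 | 9 | 7 (T1-T5 and two deep visits) | 3 / 2 |

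The expected visits are my reading of the marks. On that reading, the SAP copy fits EQ-11 and FABQ at weeks 12 and 19, and GSS-8 at all three mini-assessment types, which would include week 10. The Protocol copy shows one mark fewer in each row. If the three surveys in 12.1.3 are these mediators, any mark at another mini-assessment contradicts 12.1.3; but 12.1.3 does not say that they are.

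**Other sources in the arms.** MBSR participants complete a short EQ at sessions 2, 4 and 6 (Protocol Table 2 calls it EQ-4; the schedules list an EQ-5). The PT session questionnaires (Protocol Table 3) are the ODI, NPRS and PGIC, without FABQ. Protocol 9.3 names no mid-treatment questionnaire for acupressure.

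**The case against.** The strongest reply is that SAP 9.3 already prevents harm: it fixes the mediator in the first treatment period and bars second-stage data, so an analyst who follows it cannot pair week-19 mediators with the T3 outcome. That stands. A reader might infer that Objective 3 will report spurious mediation, with T3 pain driving a later mediator. That would happen only if the SAP's own rule were broken.

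A reader might also infer that no usable mediator data exist and that all three analyses fail. The documents do not show this. GSS-8 may already be given at week 10. EQ-11 and FABQ appear to be marked at week 12, which is late in the period but still precedes nominal T3. If week 12 is counted from baseline, as 12.1.2 indicates, and T2 runs two weeks late with treatment starting correspondingly late, week 12 becomes about the fourth treatment week. For MBSR, session 4 of 8 is the midpoint. Mediation is run within each arm, and the SAP 9.3 model has no T2 mediator term, so a short form that differs from the EQ-11 does not break the model.

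What this leaves open is which of these sources SAP 9.3 means. It names none, and no intact text confirms FABQ or EQ-11 at the first-stage midpoint.

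**Conclusion.** The conflict in timing is certain. It rests on the documents' own week numbers, and week 19 is stated consistently. The dedicated mediation assessment sits 8.5 weeks after the point SAP 9.3 specifies and 2 to 6 weeks after the outcome.

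The extent of the data gap is uncertain because it depends on schedule tables that cannot be read reliably here. The clearest gap is FABQ in the PT arm, which has no session-level substitute. EQ-11 in the MBSR arm comes next, with the session-4 short form as a possible stand-in. GSS-8 is the least exposed.

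This should be fixed but is not critical: the SAP calls Objective 3 exploratory, and the primary endpoint and the Objective 1 moderator analysis do not use these mid-treatment measurements.

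**What to change.** 1. Ensure that each SAP Table 6 mediator (EQ, FABQ, GSS-8) is collected at the week-10 mini-assessment, adding those not already there.
2. Name week 10 in SAP 9.3 as the mediator time point. For patients already past week 10, state week 12 as the fallback where it was actually collected.
3. State in SAP 9.3 which EQ form is the MBSR mediator, and that week-19 data are not used with the T3 outcome.
4. Name the three surveys in Protocol 12.1.3, and align Protocol 12.1.1-12.1.3 with both schedules so that each mediator's collection weeks are explicit.

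The cost is up to three short questionnaires added to an existing online assessment, a few minutes of participant time, and a small amendment to both documents.
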